3.1 Inclusion Criteria

3.11 Age ≥ 18 years.

3.12 Histological confirmation of expressing CD20 antigen (Cheson et al.,1999) as determined by pathology at the respective institution and central pathology review at Mayo Clinic Rochester.

NOTES:

- For Phase I, all types of B-cell lymphomas are allowed to participate.
- For phase II, only DLBCL patients are allowed to participate.
- For Phase I *only*, patients with primary mediastinal large B-cell (PMLBCL) or transformed lymphoma are allowed to participate.

ADDITIONAL NOTES REGARDING SLIDE SUBMISSION:

- Central pathology review is mandatory, but is retrospective in nature. Slides must be submitted ≤ 30 days after registration to allow for confirmation of DLBCL diagnosis and to have sufficient material for GCB/ABC assessment by a gene-expression profiling method (see Section 17).
- Patients *can* be enrolled prior to submission of slides.
- For Phase II, if central review of pathology shows that the patient does NOT have DLBCL or the amount of FFPE material is not considered sufficient for COO analysis, the patient may remain on the study but the patient should be replaced.

3.13 Measurable disease (at least 1 lesion ≥ 1.5 cm in diameter) as detected by PET/CT and as defined in Section 11.0.

3.15 Only 1 line of previous anti-lymphoma therapy is allowed and not currently receiving any other agent that would be considered as a treatment for the lymphoma. Patients must be ≥ 2 weeks from prior anti-lymphoma therapy. The use of steroids and/or rituximab up to 1 week prior to registration for management of symptoms is allowed.

3.16 ECOG Performance Status (PS) 0-2. (Form available on the ACCRU web site:

3.17 Adequate organ function as defined by the following laboratory values obtained ≤ 7 days prior to registration.:

- Absolute neutrophil count (ANC) $\geq 1500/\text{mm}^3$
- Platelet count $\geq 75,000/\text{mm}^3$
- Total bilirubin $\leq 2 \times \text{ULN}$ (unless related to lymphoma or Gilbert's disease) OR $\leq 5 \times \text{ULN}$ for subjects with documented or suspected Gilbert's disease, or related to involvement of the liver by the lymphoma.
- Aspartate transaminase (AST) and ALT (SGPT) $\leq 3 \times \text{ULN}$ unless evidence of the direct liver and/or bone involvement by lymphoma, then $\leq 5 \times \text{ULN}$
- Renal function assessed by calculated creatinine clearance as follows (see Appendix: Cockcroft-Gault estimation of CrCl):

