13.0 Treatment/Follow-up Decision at Evaluation of Patient

- 13.1 Patients who are CMR, PMR, or NMR will continue treatment per protocol for 2 cycles. The patient may receive a 3rd and 4th cycle of treatment per MD discretion.
- 13.2 Patients who develop PMD while receiving therapy will go to the event-monitoring phase.
- 13.3 Patients who go off protocol treatment for reasons other than PMD will go to the event-monitoring phase per Section 18.0.

- 13.4 Phase I Only: If a patient fails to complete the first cycle of treatment for reasons other than toxicity, the patient will be regarded as not evaluable and will be replaced.
- 13.5 A patient is deemed *ineligible* if after registration, it is determined that at the time of registration, the patient did not satisfy each and every eligibility criteria for study entry. The patient may continue treatment off-protocol at the discretion of the physician as long as there are no safety concerns, and the patient was properly registered. The patient will go directly to the event-monitoring phase of the study (or off study, if applicable).
- If the patient received treatment, all data up until the point of confirmation of ineligibility must be submitted. Event monitoring will be required per Section 18.0 of the protocol.
 - If the patient never received treatment, on-study material and the End of Active Treatment/Cancel Notification Form must be submitted. No further data submission is necessary.
- 13.6 A patient is deemed a *major violation*, if protocol requirements regarding treatment in cycle 1 of the initial therapy are severely violated that evaluability for primary end point is questionable. All data up until the point of confirmation of a major violation must be submitted. The patient will go directly to the event-monitoring phase of the study. The patient may continue treatment off-protocol at the discretion of the physician as long as there are no safety concerns, and the patient was properly registered. Event monitoring will be required per Section 18.0 of the protocol.
- 13.7 A patient is deemed a *cancel* if he/she is removed from the study for any reason before any study treatment is given. On-study material and the End of Active Treatment/Cancel Notification Form must be submitted. No further data submission is necessary.

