16.0 Statistical Considerations and Methodology

- 16.1 Overview: This is a phase I/II study designed to evaluate the safety and efficacy of the addition of lenalidomide to R-ICE (R2-ICE) for patients with first relapse or primary refractory diffuse large B-cell lymphoma. The phase I portion is designed to determine the maximally tolerated dose (MTD) and toxicity profile of lenalidomide in combination with R-ICE using the standard cohort 3+3 design. The phase II portion will utilize a one-stage design with an interim analysis to evaluate the overall response rate of R2-ICE.
- 16.11 Primary Endpoint:
The primary endpoint of the phase I portion of this trial is to assess the maximum tolerated dose (MTD) of the addition of lenalidomide to R-ICE. The primary endpoint in the phase II portion of this trial is the overall response rate after two cycles of treatment. A response will be defined as a CMR or PMR noted as the

objective status after two cycles of treatment. Throughout Section 16.0, response will be considered synonymous with “success”, unless specified otherwise. All patients meeting the eligibility criteria who have signed a consent form and have begun treatment will be evaluable for overall response, with the exception of patients who are determined to be a major treatment violation.

16.12 Sample Size:

The phase I portion of this study is expected to require a minimum of 9 and a maximum of 12 evaluable patients. DLBCL patients treated at the MTD in the phase I portion will also be included in the phase II portion. Additional evaluable patients will be accrued at the MTD dose level for a total of 45 evaluable patients in the phase II portion of this study. If a patient is found to be ineligible after enrollment due to central pathology review, they will be replaced. We anticipate accruing an additional 6 patients (2 phase I, 4 phase II) to account for ineligibility, cancellation, major treatment violation, or other reasons. Maximum projected accrual is 63 patients.

16.13 Accrual Rate and Study Duration:

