16.421 **Overall proportion of patients (%) proceeding to stem cell transplant.** **Definition:** The percentage of patients proceeding to stem cell transplant will be estimated by the number of patients who proceed to transplant divided by the total number of evaluable patients. Exact

binomial 95% confidence intervals for the true success proportion will be calculated.

- 16.422 **Complete metabolic response (CMR) rate:** The CMR rate will be estimated by the number of patients with an objective status of CMR divided by the total number of evaluable patients. All evaluable patients will be used for this analysis. Exact binomial 95% confidence intervals for the true CMR rate will be calculated.
- 16.423 **Overall survival (OS):** Survival time is defined as the time from registration to death due to any cause. The distribution of survival time will be estimated using the method of Kaplan-Meier.
- 16.424 **Percentage of Adverse Events (%) categorized based on severity using CTCAE system/organ/class criteria 4.0.** Definition: All eligible patients that have initiated treatment will be considered evaluable for assessing adverse event rate(s). The maximum grade for each type of adverse event will be recorded for each patient, and frequency tables will be reviewed to determine patterns. Additionally, the relationship of the adverse event(s) to the study treatment will be taken into consideration. The frequency and percentage of patients experiencing a particular grade/severity of adverse event would be aggregated and combined data reported.
- 16.43 Correlative Analyses:
- 16.431 **Association of histologic subtype as assessed by pathology and its association with the primary endpoint of the study.** Definition: Histologic subtype (GCB vs.ABC vs. unclassified) from tumor tissue at the start of the study will be evaluated by 2 methods: Hans algorithm by IHC and gene expression profiling using nanostring technology. For each method, the relationship between overall response (responder vs. non-responder) CR rate and subtype will be evaluated using Chi-square tests (or Fisher's exact test if the data in the contingency table is sparse).
- 16.432 **Association of SUV reduction (%) noted on interim PET/CT scan with the primary endpoint of the study.** Definition: This will be evaluated by calculating the percentage (%) SUV reduction noted on interim PET/CT scan and correlated with the overall response (responder vs. non-responder) by using a two sample t-test .

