16.45 Data & Safety Monitoring

- 16.451 The principal investigator(s) and the study statistician will review the study at least every quarter to identify accrual, adverse event, and any endpoint problems that might be developing. The Mayo Clinic Cancer Center (MCCC) Data Safety Monitoring Board (DSMB) is responsible for reviewing accrual and safety data for this trial at least twice a year, based on reports provided by the MCCC Statistical Office.
- 16.452 **Adverse Event Stopping Rule:** The stopping rules specified below are based on the knowledge available at study development. We note that the rule may be adjusted in the event of either (1) the study re-opening to accrual or (2) at any time during the conduct of the trial and in consideration of newly acquired information regarding the adverse event profile of the treatments under investigation. The study team may choose to suspend accrual because of unexpected adverse event profiles that have not crossed the specified rule below.

Accrual will be temporarily suspended if at any time we observe events considered at least possibly related to study treatment (i.e. an adverse event with attribute specified as "possible," "probable," or "definite") that satisfy any of the following:

Phase I (Includes all dose levels in phase I): By the nature of the "cohorts of three" phase I study design, toxicity (i.e., adverse events that are possibly, probably or definitely related to study treatment) stopping

rules are in place for each dose level. Specifically, if 2 or more dose-limiting toxicities (DLTs) are observed during cycle 1 at any given dose level, accrual to that dose level will be stopped, and patients will be accrued to the next lower dose level until a maximum of 6 patients are treated at the lower level. Note that a DLT that affects dose escalation is only that which is observed in the first cycle of treatment. However, all cycles will be reviewed and the study team will determine whether the dose level needs to be adjusted for future patients if ≥ 1 in the first 3 patients OR ≥ 2 in the first 6 patients experience a grade 4 or higher non-hematologic adverse event at least possibly related to treatment over all cycles at any given dose level

Phase II (includes all phase II patients, including Phase I patients treated at the MTD):

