- if 5 or more patients in the first 15 treated patients experience a grade 4 or higher non-hematologic adverse event at least possibly related to treatment, excluding febrile neutropenia and dehydration.
- if after the first 15 patients have been treated, 30% of all patients experience a grade 4 or higher non-hematologic adverse event at least possibly related to treatment, excluding febrile neutropenia and dehydration.

We note that we will review grade 4 and 5 adverse events deemed “unrelated” or “unlikely to be related”, to verify their attribution and to monitor the emergence of a previously unrecognized treatment-related adverse event.

16.5 Results Reporting on ClinicalTrials.gov: At study activation, this study will have been registered within the “ClinicalTrials.gov” website. The Primary and Secondary Endpoints along with other required information for this study will be reported on ClinicalTrials.gov. For purposes of timing of the Results Reporting, the initial estimated completion date for the Primary Endpoint of this study is 2 years after the study opens to accrual. The definition of “Primary Endpoint Completion Date” (PECD) for this study is at the time the last patient registered has completed the response evaluation after two cycles of treatment.

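### Section 16.424 reports phase II adverse event rates in eligible patients only, so treated patients later found ineligible drop out of rates that the stopping rule would count them in

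*Combined protocol and SAP*

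**What the plan says.** Section 16.424, the adverse event secondary endpoint, applies two filters, eligibility and a start of treatment: "All eligible patients that have initiated treatment will be considered evaluable for assessing adverse event rate(s".

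The phase II stopping rule in 16.452 is introduced as "Phase II (includes all phase II patients, including Phase I patients treated at the MTD". Accrual is suspended "if 5 or more patients in the first 15 treated patients experience a grade 4 or higher non-hematologic adverse event", or "if after the first 15 patients have been treated, 30% of all patients experience a grade 4 or higher non-hematologic adverse event", in each case counting events at least possibly related to treatment and leaving out febrile neutropenia and dehydration. Neither limb mentions eligibility.

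Several sections show that patients can be treated first and found ineligible afterwards:

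- Section 3.12: "Central pathology review is mandatory, but is retrospective in nature". Slides are due within 30 days of registration. For a phase II patient who proves not to have DLBCL, or whose tissue is insufficient for cell-of-origin analysis, "the patient may remain on the study but the patient should be replaced".
- Section 6.36: treatment starts within 14 days of registration.
- Section 16.12: "If a patient is found to be ineligible after enrollment due to central pathology review, they will be replaced".
- Section 13.5: a patient is ineligible if any entry criterion proves not to have been met at registration. "If the patient received treatment, all data up until the point of confirmation of ineligibility must be submitted", and the patient then moves to event monitoring.

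**The concern.** Describing the toxicity of the combination is secondary objective 2.23, and 16.5 commits the trial to posting the secondary endpoints. Restricting a response rate to eligible patients can be defended, because disease type defines that question. The argument does not carry over to toxicity: a diagnosis revised after the event does not undo the exposure. Leaving such patients out is a selection made after treatment has begun.

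The plan is also inconsistent with itself. Accrual could be suspended because of events in patients who are then missing from the reported rates, and a reader could not reconcile the published table with the suspension.

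**Working it through.** **Inputs.** Phase I maximum 12, phase II evaluable 45, allowance 6 (2 in phase I, 4 in phase II) and maximum accrual 63, all from 16.12. Stopping limits of 5 in the first 15, then 30%, from 16.452. The figure of 10 eligible patients with an event is an assumption for illustration.

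**1. The plan's own figures reproduce.** Accrual: 12 + 45 + 6 = 63, as stated. For the design in 16.31, the probability of a positive result is the sum over x = 10 to 20 of P(X = x) × P(Y ≥ 25 − x), with X ~ Bin(20, p) and Y ~ Bin(25, p). This gives 0.0903 at p = 0.45 (stated 0.090) and 0.9001 at p = 0.65 (stated 0.900). Early stopping, P(X ≤ 9), is 0.5914 and 0.0532 (stated 0.591 and 0.053). None of these depends on the safety population.

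**2. Can a treated patient become ineligible?** Yes. Treatment must start by day 14 after registration and slides may arrive up to day 30, so treatment can begin before central review is possible. Sections 13.5 and 16.12 both provide for the case. No section returns such a patient to the 16.424 rates.

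**3. Effect on a reported rate.** Suppose all 4 phase II allowance patients are treated and later found ineligible. Treated = 45 + 4 = 49. With 10 events among the 45 eligible and j among the 4 dropped:

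- reported under 16.424: 10/45 = 22.2%
- all treated, (10 + j)/49: j = 0 gives 10/49 = 20.4%; j = 4 gives 14/49 = 28.6%

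The eligible-only rate can therefore be too high or too low.

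**4. Effect when the 30% limit is just reached.** With k dropped patients, N = 45 + k and the limit is the smallest whole number c with c/N ≥ 0.30. The eligible-only rate lies between (c − k)/45 and c/45.

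| k | N | c | all treated | eligible only |
|---|---|---|---|---|
| 1 | 46 | 14 | 30.4% | 28.9% to 31.1% |
| 2 | 47 | 15 | 31.9% | 28.9% to 33.3% |
| 3 | 48 | 15 | 31.3% | 26.7% to 33.3% |
| 4 | 49 | 15 | 30.6% | 24.4% to 33.3% |

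**5. Effect at the first-15 limit.** 5/15 = 33.3% suspends accrual. If one of the five patients with an event is later found ineligible, the eligible-only figure is 4/14 = 28.6%. If a patient without an event is dropped instead, it is 5/14 = 35.7%.

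These counts leave aside any phase I patients with other B-cell lymphomas treated at the MTD.

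**The case against.** The strongest reply is that little depends on this sentence. Section 16.424 is descriptive, with no test or decision attached. Events in treated ineligible patients are collected up to confirmation of ineligibility, fall under expedited reporting (10.4) and are within the quarterly and DSMB reviews (16.451). Eligibility is verified before registration is accepted (6.32), so few failures other than pathology should arise, and nothing in the documents suggests that a change of histology tracks toxicity. All of this stands, and it keeps the point modest.

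Two further objections also stand. The first concerns scope. The note in 3.12 covers only phase II patients with a non-DLBCL diagnosis or insufficient tissue and does not itself call them ineligible, so it is unclear whether 16.424 drops a patient replaced only for insufficient tissue. How that note fits with 13.5, which sends ineligible patients straight to event monitoring, needs to be reconciled by the sponsor. The second concerns data. Section 13.5 requires data only up to confirmation of ineligibility, and the event-monitoring forms in 18.1 include no routine adverse event form. Adding these patients to the denominator without addressing that cut-off could itself lower the rates. The late-event instructions in 10.54 and expedited reporting fill the gap only in part.

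None of this answers the mismatch in wording between 16.424 and 16.452.

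**Conclusion.** The point holds as a narrow one about the reporting population. As written, 16.424 omits real exposures from a stated secondary endpoint, while the phase II stopping rule counts them. Under the plan's allowance the loss is at most about 4 of 49 treated phase II patients. That upper end assumes that none of the 4 is a cancellation or an eligible patient with a violation, and the allowance is a projection, not a cap.

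Stronger readings that a reader might infer are not supported:

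- *That 6 of 63 (9.5%) would be dropped.* The allowance includes cancellations, who by 13.7 were never treated, and major violations, whom 16.424 does not exclude.
- *That toxicity will be understated.* The range of 20.4% to 28.6% lies on both sides of 22.2%. Patients who breach organ-function criteria could plausibly have more toxicity, but the documents give no frequency for such breaches.
- *That safety monitoring fails or events are lost.* Suspension decisions already use treated patients; only the reported rates are affected.
- *That the phase I summaries share the defect.* Sections 16.231 and 16.232 contain no eligibility filter.

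**What to change.** Replace the population sentence in 16.424 with: *All patients who receive at least one dose of any study drug are evaluable for adverse events, regardless of eligibility or replacement.* This matches the treated population already used in 16.452. Eligible-only rates can stay as an optional supplementary table.

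In the same amendment, deal with 13.5 in one of two ways: state its data cut-off alongside the rates, or align 13.5 and the form schedule in 18.1 so that routine adverse event data for these patients cover the same period as for other treated patients. Sections 16.231 and 16.232 need no change.

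The cost is one sentence in 16.424 plus a footnote, or a small edit to 13.5 and 18.1 with some extra data collection. Significance level 0.090, power 0.900, 45 evaluable and 63 accrued are unchanged. The downside is a slightly larger safety table and, if the cut-off is kept, possibly shorter adverse event follow-up in the added patients.

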1.3 Rationale for the Current Study

Despite various effective salvage chemotherapy regimens available in the primary-refractory/first-relapse setting, the overall response rate achieved for patients with DLBCL could still be improved upon to increase the proportion of patients going for a SCT. The goal of our study, therefore, would be to determine if the addition of lenalidomide to the R-ICE chemoimmunotherapy regimen (R2-ICE) would lead to a clinically meaningful improvement in the overall response rates (ORR) for patients with primary-refractory/first-relapse DLBCL. As a secondary end point, we would also look at the complete metabolic response (CMR) rates.

As a secondary objective at the time of analysis, following the algorithm developed by Hans et al, we would analyze patient outcomes based on their subtypes (GCB versus non-GCB subtypes), international prognostic index (IPI) and the timing of their recurrence (≤ 12 months versus > 12 months). (Hans, Weisenburger et al. 2004; Thieblemont, Briere et al. 2011). In particular our focus would be to see if it leads to improvement in the non-GCB subtype given the overall adverse outcome in this subgroup of patients. We would use nanostring technology here in addition to the traditional Hans algorithm to classify patients into GCB and non-GCB subtypes. Additionally, we would also evaluate and compare the rates the stem cell mobilization achieved in patients receiving R2ICE chemoimmunotherapy compared to historical controls.

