1.5 Correlative Research

1.51 Impact of DLBCL molecular subtype on efficacy of R2-ICE: DLBCL is a heterogeneous disorder with different subtypes based on Hans algorithm: germinal center B-cell type (GCB) and activated B-cell type (ABC). The latter group is often included in non-GCB type in immunohistochemistry (IHC) based classification algorithms. This classification is based on the so called cell-of-origin (COO) grouping system (Scott, 2014). The ABC (non-GCB subtype) has been associated with worse outcome both in the pre- and post- rituximab era. Retrospective analysis of the outcomes of patients with GCB vs non-GCB DLBCL treated with salvage lenalidomide at 4 academic institutions was recently performed (Hernandez-Ilizaliturri et. al., 2011). Forty patients with relapsed/refractory DLBCL were included (24 men; 16 women; median age, 66 years; median of 4 prior treatments, including rituximab chemotherapy). Patients were classified as GCB (n = 23) or non-GCB (n = 17) DLBCL according to the Hans algorithm. The subgroups were similar in terms of stage, IPI score, prior number of treatments, and rituximab resistance. A significant difference in clinical response to lenalidomide was observed in non-GCB versus GCB patients. ORR was 52.9% versus 8.7% (P = .006); CR rate was 23.5% versus 4.3%. Median PFS was 6.2 versus 1.7 months (P = .004), although no difference in OS was observed between non-GCB and GCB DLBCL patients. There is also evidence to suggest that the DLBCL subtype may have an impact on lenalidomide efficacy in the upfront therapy on work done by our group earlier (Nowakowski et. al, 2011, and Nowakowski, 2014) ; however, its impact in the relapsed and primary-refractory setting still remains to be determined.

In the current study as part of the correlative studies, we will assess impact of DLBCL subtype on the overall response rates achieved for patients with primary-refractory/first-relapse lymphoma. In addition to using immunohistochemistry as proposed by the Hans algorithm, we would further employ gene expression profiling using nanostring technology for classification of these subtypes (Scott, 2014).

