2.3 Correlative Research

- 2.31 To evaluate ORR based on GCB versus non-GCB subtypes. Hans algorithm by immunohistochemistry and gene expression profiling using nanostring technology for classification of these subtypes will be used (Scott, 2014). Outcomes will also be compared based on patients' IPI scores and time of recurrence of lymphoma.
- 2.32 To evaluate ORR based on percent SUV reduction and percent anatomic size reduction on interim PET/CT scans.
- 2.33 To evaluate ORR based on Minimal Residual Disease (MRD) detection (positive vs. negative) and quantification after 2 cycles of treatment.
- 2.34 Future tissue and blood based studies: Additionally, samples collected during this study would be stored for future and ongoing research. (see details below).

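### Goal 2.31 asks for ORR in GCB versus non-GCB, but section 16.431 tests three subtype groups and names no analysis of that two-group contrast

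*Combined protocol and SAP*

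**What the plan says.** The purpose is stated with two groups. Goal 2.31 reads "To evaluate ORR based on GCB versus non-GCB subtypes" and continues "Hans algorithm by immunohistochemistry and gene expression profiling using nanostring technology for classification of these subtypes will be used". Section 1.3 agrees: "We would use nanostring technology here in addition to the traditional Hans algorithm to classify patients into GCB and non-GCB subtypes". It puts the particular focus on the non-GCB group.

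The analysis is stated with three. Section 16.431 says "Histologic subtype (GCB vs.ABC vs. unclassified) from tumor tissue at the start of the study will be evaluated by 2 methods", the two methods being Hans by IHC and nanostring gene expression. For each method, subtype is related to response by a chi-square test, or by Fisher's exact test if the table is sparse. The section does not mention non-GCB, and it gives no rule for placing unclassified patients in a GCB versus non-GCB comparison.

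On Hans, section 1.51 names two classes, GCB and ABC, and says of ABC: "The latter group is often included in non-GCB type in immunohistochemistry (IHC) based classification algorithms". It also reports the cited lenalidomide series: "Patients were classified as GCB (n = 23) or non-GCB (n = 17) DLBCL according to the Hans algorithm". No section describes an unclassified result from Hans.

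**The concern.** The test specified is not the test of the question asked. A three-group test asks whether any of the three response rates differs from the others. It can be significant because ABC differs from unclassified while GCB and non-GCB respond alike. It also gives no estimate of the GCB versus non-GCB difference.

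The same three labels are applied to both methods, although the documents give Hans only two classes. Read literally, Hans would produce a two-group comparison and nanostring a three-group one, under a single goal.

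What is at stake is how the subtype result is read. With about 45 patients and no stated rule, someone would have to decide, possibly after seeing responses, whether unclassified patients are pooled with ABC, left out or kept as a third group. That choice can change the answer.

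**Working it through.** **1. Plan figures.** The plan gives no power, significance level, subtype mix or subtype ORR for 16.431. Its only phase II power table, in 16.32, concerns the primary endpoint. That table reproduces (0.090 at a true ORR of 45%, 0.900 at 65%) but has no bearing here.

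**2. Classes by method.**

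| Source | Hans | Nanostring |
|---|---|---|
| 1.3 and goal 2.31 | GCB, non-GCB | GCB, non-GCB |
| 1.51 | GCB, ABC (ABC often placed within non-GCB) | not listed |
| Cited series in 1.51 | 23 GCB + 17 non-GCB = 40, the whole series | not used |
| 16.431 | GCB, ABC, unclassified | GCB, ABC, unclassified |

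If Hans returns no unclassified cases, its third row is empty and the table reduces to 2x2 with no degree of freedom lost. What follows therefore concerns nanostring.

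**3. Method.** N = 45 evaluable (16.312). Assumed: two-sided 5% level, fixed group sizes n_i and true ORRs p_i.

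- Pooled ORR in non-GCB = (n_ABC × p_ABC + n_U × p_U) / (n_ABC + n_U).
- Rejection probability = sum over all (x1, x2, x3) of the product of C(n_i, x_i) × p_i^x_i × (1 − p_i)^(n_i − x_i), counting tables with exact p ≤ 0.05.
- Two groups: Fisher 2x2, GCB against ABC plus unclassified. Three groups: Fisher-Freeman-Halton.

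**4. Does the three-group test answer goal 2.31?** Take 20 GCB, 15 ABC and 10 unclassified, with ORRs of 65%, 80% and 42.5%. The pooled non-GCB ORR is (15 × 0.80 + 10 × 0.425) / 25 = (12 + 4.25) / 25 = 65%, equal to GCB, so the contrast in goal 2.31 is null.

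- Three-group test rejects: 0.38
- Two-group test rejects: 0.03

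The three-group test is not faulty, since the three rates do differ. It is answering another question.

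**5. Is there a fixed power cost?** Take 20 GCB, 20 ABC and 5 unclassified.

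| ORR GCB / ABC | ORR unclassified | Two-group | Three-group | Difference |
|---|---|---|---|---|
| 45% / 80% | 80% (like ABC) | 0.634 | 0.553 | +0.08 |
| 45% / 80% | 62.5% (midway) | 0.524 | 0.532 | −0.01 |
| 45% / 80% | 45% (like GCB) | 0.417 | 0.593 | −0.18 |
| 50% / 80% | 80% | 0.506 | 0.423 | +0.08 |
| 50% / 80% | 65% | 0.408 | 0.412 | −0.00 |
| 50% / 80% | 50% | 0.318 | 0.468 | −0.15 |
| 50% / 90% | 90% | 0.833 | 0.753 | +0.08 |
| 50% / 90% | 70% | 0.714 | 0.735 | −0.02 |
| 50% / 90% | 50% | 0.574 | 0.798 | −0.22 |

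Other inputs widen the spread. With a 26/15/4 split and 50% versus 80%, by chi-square and with unclassified like ABC, power is 0.569 (two groups) against 0.411 (three). With 22/16/7 and 40% versus 90%, by exact tests and with unclassified like GCB, it is 0.629 against 0.906. The sign turns on a quantity for which the documents give no data.

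**The case against.** The strongest reply is that keeping ABC and unclassified apart preserves information. Section 1.51 ties the worse outcome to ABC, which it equates with the non-GCB subtype, so GCB against ABC may be the contrast of real interest, and pooling can blur it. Three-group counts can also be collapsed to two groups later, and no decision depends on this analysis. All of that stands. It argues for keeping the three-group results, but it does not supply the missing two-group analysis or say where unclassified patients belong in it.

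Three stronger readings are tempting, and the documents do not support them:

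- **The Hans table cannot be built.** Section 1.51 itself labels the Hans classes GCB and ABC, so only the unclassified level lacks support, and an empty row simply drops out. A firmer statement about the algorithm would need an outside source.
- **The three-group test costs a set amount of power, about 8 points.** That figure arises when unclassified patients are assumed to respond like ABC. It vanishes if they respond midway and reverses if they respond like GCB.
- **The two methods can never be compared, or a correct table would show greater benefit from lenalidomide in non-GCB.** Collapsing restores the comparison. In a single-arm trial, either table shows association with response, not differential benefit.

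**Conclusion.** The mismatch is real and needs no assumption: goal 2.31 and section 1.3 pose a two-group question for both methods, and 16.431 specifies a three-group test for both, with no link between them. For Hans this is a labelling gap. For nanostring the planned test does not target or estimate the stated contrast. The 38% against 3% rejection rates illustrate this for one assumed mix, set of ORRs and 5% level; they do not predict what this trial will show.

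No power loss or gain should be attached to the point. The issue is minor: the analysis is correlative, and the phase II go/no-go rule in 16.31 uses overall ORR alone.

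**What to change.** Reword 16.431 as follows.

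- For each method, the analysis answering goal 2.31 is GCB versus non-GCB: a 2x2 Fisher exact test, with the ORR difference and its 95% CI.
- Hans: label the classes GCB and non-GCB.
- Nanostring: define non-GCB as all patients not classified GCB, fixed before responses are examined. Add a sensitivity analysis of GCB versus ABC that omits unclassified patients.
- Keep the three nanostring ORRs and the three-group test as supportive results.

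The cost is wording only, with no change to sample size, data collection or the primary decision rule. The downside is that pooling dilutes a GCB versus ABC difference if unclassified patients respond unlike ABC. The sensitivity analysis is there to show that.
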